2.0 Background and Rationale

Diverticulitis is one of the most common gastrointestinal indications for inpatient hospital admission, outpatient clinic and emergency room visits, and colon surgery.^{1, 2} At least 20% of individuals with an initial episode of diverticulitis will have one or more painful and unpredictable recurrences.³ The risk of recurrence increases with each subsequent episode.³ Unfortunately, there is no proven pharmacologic means to decrease the risk of diverticulitis.⁴ Currently, secondary prevention relies on segmental colectomy, which is associated with a ~10% risk of major complications and does not eliminate the possibility of future attacks.⁵⁻⁸ In the face of the enormous burden of recurrent diverticulitis, secondary prevention is a high priority.

Diet and lifestyle factors are modifiable targets for prevention of diverticulitis. Multiple large, prospective cohort studies, including work from our group, have identified low dietary fiber, high red-meat intake, and a Western dietary pattern as risk factors for incident diverticulitis.⁹⁻¹³ Physical inactivity, obesity, smoking, and nonsteroidal anti-inflammatory drug use also increase risk.¹⁴⁻¹⁹ An observational study of 51,000 men examining the joint contribution of multiple modifiable risk factors found a linear relationship between number of low-risk factors and diverticulitis incidence. Adherence to a low-risk profile (<51g/day red meat, >23g/day fiber, 2 hours exercise/week, normal BMI and never smoked) decreased the risk of incident diverticulitis by nearly 75% (RR 0.27, 95% CI 0.15-0.48).²⁰ However, these modifiable risk factors have not been evaluated for secondary prevention. Based on the indirect nature of the evidence, U.S. guidelines conditionally recommend diet and lifestyle changes in individuals with a history of diverticulitis. As part of the Dietary Guidelines for Americans, the USDA developed a Healthy Mediterranean-style Food Pattern²¹ that includes the main dietary components associated with primary prevention of diverticulitis and may be effective for secondary prevention. However, barriers to adherence relating to cost, cultural preferences, and food restrictions need to be addressed to consider it a practical intervention in a clinical setting.

Growing evidence suggests an interaction between diet, lifestyle, the gut microbiota, chronic inflammation, and episodes of diverticulitis. Cross-sectional studies indicate that gut microbial composition differs in patients with diverticulitis compared with controls,²²⁻²⁵ and diet and lifestyle are known to influence the gut microbiome.²⁶⁻²⁹ Prediagnostic inflammatory markers (interleukin-6 [IL-6]) and a diet with high inflammatory potential were associated with increased risk of diverticulitis.³⁰ Thus, serum and stool biomarkers may identify high-risk individuals who are likely to respond to preventative interventions. Greater use of the Mediterranean diet decreases dietary inflammation scores and levels of circulating biomarkers of inflammation^{31, 32} and it is effective in the prevention of cardiovascular disease^{33, 34} and certain cancers.³⁵

2.1 Rationale

As our preliminary data indicate, diets that promote inflammation increase the risk of diverticulitis, and are therefore potential targets for secondary prevention. Dietary patterns account for the combined influence of multiple dietary components on disease risk, more closely resemble real world dietary practices, and are more readily translated into public health interventions.¹³⁰ A Mediterranean diet is more strongly associated with reduced CRP and other cardiometabolic risk factors than other diet patterns such as AHEI and DASH,⁷² and is inversely associated with inflammatory diet scores. It also shares many features with other diets that are inversely associated with incident diverticulitis, including the AHEI and prudent pattern. A USDA Med-style Food Pattern is prominently featured in the widely disseminated Dietary Guidelines for America 2020-2025 and is well known to health professionals.¹³¹ Therefore, we hypothesize that a USDA Med-style Food Pattern diet will reduce the risk of recurrent diverticulitis and the level of inflammatory markers more than a high- fiber diet or fiber supplementation and will be

feasible to implement in a large-scale RCT, as well as clinical practice and public health interventions.

We will study three biomarkers involved in systemic inflammation and implicated in chronic disease. Our prior work linked diet, CRP and IL-6 (but not TNFR1B) to incident diverticulitis.³⁰ CRP and IL-6 are major inflammatory markers implicated in chronic disease and are associated with the inflammatory potential of diet.³⁰ In this study, we will measure IL-6, IL-1 β and IL-10 primary pro and anti-inflammatory cytokines, respectively.¹³²⁻¹³⁴ We will also collect blood samples for future biomarker studies that are outside the scope of this pilot feasibility study. Future biomarker work could explore additional inflammatory cytokines such as CRP, fat derived hormones such as adiponectin and markers of intestinal permeability such as lipopolysaccharide (LPS), as well as repeat multiplex assays (e.g., of IL-6, IL-1b, IL-10) and blood-based metabolome to examine various pathways that are hypothesized to link diet, chronic inflammation, and diverticulitis.

Fecal calprotectin is a protein found in the cytoplasm of neutrophil granulocytes that is released in the stool when the intestinal tract—the colon in particular—is inflamed.¹³⁵ It is resistant to bacterial degradation and is easily measured in stool.^{136, 137} It is a more sensitive and specific marker of intestinal inflammation when compared with plasma erythrocyte sedimentation rate (ESR) and CRP,^{136, 138} and can detect subclinical inflammation. It is commonly used to diagnose and monitor inflammatory bowel disease.^{139, 140} Fecal calprotectin is also elevated in acute diverticulitis,¹⁴¹ and in a study of 48 patients followed every 2 months after recovery, it was predictive of recurrence.¹⁴² In this study, a semi-quantitative test was used (<15 μ g/g, \geq 15 μ g/g-60 μ g/g, >60 μ g/g). Seventeen (37%) of patients had increased fecal calprotectin (>15 μ g/g) after a normal test following treatment for acute diverticulitis; 7 of 8 (88%) of patients with recurrence had an elevated fecal calprotectin during follow-up. Studies of healthy controls and patients with inflammatory bowel disease indicate that fiber intake and the Mediterranean diet are associated with decreases in fecal calprotectin.^{137, 143} Therefore, we have selected fecal calprotectin as an innovative and plausible biomarker that may predict risk of recurrent diverticulitis and be more sensitive than plasma biomarkers. Collection of samples will provide data on the feasibility of stool collection within a larger diet trial. We also plan to collect and store stool for future work on the gut microbiome and metabolome in diverticulitis that is outside the scope of this pilot study.

3.0 Study Aims and Methods

3.1 Study Aims

Aim 1. Conduct a randomized trial (n=75) of the USDA Healthy Med-style Food Pattern intervention versus standardized guidance on fiber intake for patients with diverticulitis to determine feasibility of a larger-scale effectiveness trial focused on long-term clinical outcomes (recurrence and complications). We will examine willingness to randomize and assess adherence to USDA Healthy Med-style Food Pattern.

Aim 2. Explore plasma inflammatory markers in a subset of participants (n=40) (IL-6, IL-1, IL-1 β) and fecal calprotectin as short-term, intermediate inflammatory biomarkers of response to treatment and collect samples for future biomarker study.

The hypotheses underlying the IMPEDE trial include 1) A large-scale trial of the USDA Med-style Food Pattern will be feasible (high rate of patient willingness to be randomized, high rate of adherence to the intervention, improvement in Med-style food pattern scores assessed by a well-characterized food frequency questionnaire (FFQ) [measure of extent of use of the Mediterranean diet], acceptability of study survey burden and follow-up). 2) A USDA Med-style Food Pattern reduces serum and fecal biomarkers of inflammation more than standardized

recommendation to encourage a high-fiber diet. Based on prior studies, we expect reductions in these biomarkers will correlate to lower rates of recurrent diverticulitis.

3.2 Methods

This is a feasibility-focused, patient-level randomized trial of an intervention promoting the USDA Healthy Med-Style food pattern versus standardized guidance on fiber intake (standard educational materials related to a high-fiber diet) in patients with a history of diverticulitis. This trial will assess and address barriers to the eventual large-scale trial and lay groundwork for that trial that will focus on the risk of recurrent diverticulitis and other clinical outcomes. We will also compare changes in serum and stool biomarkers of inflammation that are proximal endpoints in the causal path relating a Mediterranean diet pattern's anti-inflammatory properties and recurrence of diverticulitis.

Research Setting

[figure not shown]
The proposed work will use the infrastructure of the Comparative Effectiveness Research Translation Network (CERTAIN), a collaborative of dozens of health systems across the US with a successful track record of conducting large-scale randomized and observation cohort studies. The CERTAIN diverticulitis research network, described in more detail in the UW Facilities and Resources description, supports our diverticulitis studies (e.g., DEBUT and COSMID) and will provide the setting for the conduct of IMPEDE.

The University of Washington's (UW) Surgical Outcomes Research Center (SORCE) will lead a Clinical Coordinating Center (CCC). The UW Center for Biomedical Statistics (CBS) will serve as the Data Coordinating Center (DCC).

4.0 Study Flow, Participant Screening and Enrollment

4.1 Overview of Study Flow

Figure 1: IMPEDE Trial Design

4.2 Participant Screening

Patients presenting to University of Washington Medicine gastroenterology and surgery clinics at UWMC and Harborview will be screened, remotely and/or in-person, by the research team. Patient-facing flyers will be posted at the clinic locations to allow potential participants to ask their clinician about the study or to access study information via a link/QR code/study contact information. Patients deemed eligible via initial clinician/research team pre-screening will have eligibility confirmed. They will then be given time to ask questions about the study to determine whether they are interested in participating.

Patients will also be able to begin a self-screening process on the Surgical Outcomes Research Center (SORCE) website, guiding them through simple yes/no eligibility questions to determine if the trial might be right for them (study eligibility from screening form). Patients will have the opportunity to review a consent form but will be contacted by a research team member for a consent call before they are able to sign and provide consent to participate. A study investigator will confirm eligibility before randomization, but no clinic visit will be required of those patients interested in enrolling in this manner. To be considered for participation, patients must have had a confirmed diagnosis of diverticulitis by a physician, with medical records to be accessed by study physician(s) to confirm.

The study team will also contact patients previously seen for diverticulitis and screened for other trials. Basic eligibility information will be visible to the research team through medical record screening.

4.3 Inclusion Criteria

1. Adult ≥ 18 years;
2. Patients presenting (or recently presented) to gastroenterologist or surgeons or accessing study website after recovery from an episode of diverticulitis (within the prior 18 months), either the index episode or recurrent.
3. Ability to provide written informed consent in English.

4.4 Exclusion Criteria

Participants must not have any of the following exclusion criteria:

1. Unable or unwilling to return for specimen collection visits or be contacted for and/or complete research surveys;
2. Currently incarcerated in a detention facility or in police custody (patients wearing a monitoring device can be enrolled) at baseline/screening;
3. Last episode of acute diverticulitis currently unresolved (i.e., on antibiotics for diverticulitis; drain in place)
4. Intolerance/allergy to the main components of the Med-style food pattern;
5. Surgery for diverticulitis within past 6 months without an episode of diverticulitis post-surgery
6. Planned elective surgery in next 6 months

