5.2 Research Assessments

5.2.1 Baseline Assessment (Index Encounter)

The Baseline Assessment as listed in Table 1 should be completed in-person or online and *prior to revealing the participant's random treatment assignment*; however, research coordinators are asked to document when the participant became aware of their assignment, should it be revealed prior to completion of the Baseline Assessment.

- Survey questions will be presented in the order of importance in the event that the participant is unable to complete the full battery of questionnaires.
- Collection and Measurement of Inflammatory Markers: We will collect and store blood samples on all participants. For the exploratory aim of this pilot study, we will measure inflammatory markers in plasma drawn in up to 40 participants. Blood samples will be collected in purple top EDTA tubes (EDTA plasma will be collected and stored for future studies) and immediately processed at room temperature.
- Collection of Stool for Measurement of Fecal Calprotectin and Future Studies: Participants may collect stool samples for future microbiome and metabolome analyses using an easy-to-use kit including catchment materials placed under the toilet lid and a small spatula/spoon. For stool collection, the spatula/spoon will be dipped into the fecal material and 1-5 g (peanut sized sample) will be obtained and placed in a clean, screw-top vial. Another small sample will be obtained and placed in another identical vial containing ethanol with instructions to screw lid tightly and shake. To optimize stability of the specimens, the vials should be refrigerated until shipping or transport.

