5.6 Compensation

5.6.1 Participant Compensation

Participants will be paid up to \$150 for completing the research assessments described in Table 1 (Section 5.0). Payment will be provided on a pro-rated, weighted fashion: \$25 for the Baseline Assessment, up to \$20 for Quarterly Assessments through 12 months. Participants will receive \$10 for the biospecimen collection at baseline, \$15 at 6 months and \$20 at 12 months. Compensation will be distributed to participants by UW research staff unless other arrangements have been made.

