6.0 Outcome Assessments

6.1 Primary and Secondary Outcomes

Patient Reported Outcomes (PROs) will be assessed for adults using both generic and disease-specific surveys utilizing the QoL instruments in Table 2.

Table 2. Primary and secondary outcomes and intervention related process measures.

| Primary or Secondary | Name of Outcome | Specific Measure to Be Used | Time Point |
|----------------------|---|--|------------------------|
| Primary | Willingness to enroll | Enrolled/approached | Baseline |
| Primary | Adherence to USDA Med-Style Food Pattern | USDA Med-style Pattern score calculated from the NASR FFQ. ¹⁶¹ | Baseline, 6, 12 months |
| Primary | Participant retention | Proportion enrolled and retained at 3, 6, 9 and 12 months | 3, 6, 9 and 12 months |
| Primary | Interaction with on-line program | Number of times accessed | Bi-weekly |
| Primary | Engagement with nutrition services | Number of sessions with dietician | Quarterly |
| Secondary | Plasma, IL-6, IL-10, IL-1 β , fecal calprotectin | Concentration | Baseline, 6, 12 months |
| Secondary | Diverticulitis events | Self-reported (presumed), subset of those resulting in healthcare utilization (e.g., hospitalization, surgery). | Quarterly |
| Secondary | NSQIP-defined complications, a subset of which are serious adverse events to be reported to ISM | Standardized assessment-serious events defined as death, cardiac arrest, myocardial infarction, pneumonia, progressive renal insufficiency, acute renal failure, pulmonary embolism, deep vein thrombosis, return to operating room, serious site infections | Quarterly |
| Secondary | DVQOL ⁶⁵ | A 17-item questionnaire that assesses four domains: symptoms, concerns, emotions, and behavior changes related to diverticulitis. | Baseline, 6, 12 months |
| Secondary | GIQLI ¹⁵⁹ | A 36-item questionnaire that assesses five domains: gastrointestinal symptoms, physical function, emotional well-being, social well-being, and perception of medical treatment measured by a single item question. | Baseline, 6, 12 months |

| | | | |
|-----------|--------------------------------|--|------------------------|
| Secondary | IPAQ Short Form ¹⁶⁹ | A validated 7-item questionnaire: moderate and vigorous physical activity, walking, and sitting in the past 7 days | Baseline, 6, 12 months |
| Secondary | Time in healthcare | Days missed from work/school, ED/hospital encounters, diverticulitis-related diagnostic/therapeutic interventions | 3, 6, 9 and 12 months |

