8.2 Study Feasibilities Measures

We will assess willingness to randomize as the number of eligible patients that randomized divided by the number of eligible patients (Aim 1). We will provide descriptive statistical summaries of time to complete survey materials, time interacting with the USDA Med-style Food Pattern platform, and changes in estimated weekly meal expenses. These data will be used to inform the future large-scale trial including the number of study sites, recruitment rate/study duration and amount of coordinator effort. The rate of willingness to randomize is unknown but as long as it is at least 20% our study will be successful. We would also want at least 50% of those willing to randomize to be willing to give a blood sample and at least half of those to give stool.

8.3 Treatment Fidelity and Adherence:

The Fred Hutch FFQ is a standard method of dietary intake assessment that has been used in several large-scale cohort studies including the Women’s Health initiative.^{153, 154} The degree of adherence with the USDA Healthy Med-style Food Pattern (Aim 1) will be ascertained by assigning point scores based on the estimated daily amounts of the recommended food groups and subgroups habitually consumed. Full points will be awarded to diets that meet all the

recommendations and partial points to diets that do not. Given that the USDA Healthy Med-style Food Pattern provides recommended amounts for relevant food groups, the adherence score will be based on food consumption data normalized per 100 kcal, much along the lines of the Healthy Eating Index (HEI). The HEI is a 100-point score that measures adherence to the DGA and is the standard measure of diet quality in the US. This approach represents an advance over the 14-item food frequency MEDAS score, which ranks adherence to the Med-style diet pattern using 3 cutpoints: ≤ 7 , 8–9, or ≥ 10 (maximal adherence).¹⁴⁵ The data derived will help us understand the central tendency and variability in Med-style food pattern scores which is critical for determining the sample size of a future trial. Degree of adherence to the different aspects of the medical management regimen will also be used to define per-protocol analysis and be considered as potential mediators and/or effect modifiers in explanatory regression models

8.4 Signal Assessment for Biomarkers:

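### The 50% blood-sample aim is read only among patients who already accepted specimen visits, and the primary willingness outcome has two different denominators

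*Combined protocol and SAP*

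**What the plan says.** Section 4.4, criterion 1, excludes anyone "Unable or unwilling to return for specimen collection visits or be contacted for and/or complete research surveys". Two kinds of reason, specimen visits and survey or contact burden, sit in one item.

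Section 4.2 states for the website route that "A study investigator will confirm eligibility before randomization". Section 4.5 has the coordinator and a member of the medical team check the criteria before consent.

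Section 8.2 defines willingness to randomise as the "number of eligible patients that randomized divided by the number of eligible patients" and ties the pilot's success to a rate of at least 20%. It adds a wish for "at least 50% of those willing to randomize to be willing to give a blood sample", with at least half of those also giving stool. Table 2 (section 6.1) lists willingness as a primary outcome but measures it as "Enrolled/approached".

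The surrounding text on blood is mixed. Section 5.2.1 says "We will collect and store blood samples on all participants", while section 5.6.1 pays a separate amount "for the biospecimen collection at baseline" and at each later collection, and 8.2 would be content with half.

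Section 8.4 expects the biomarker work to inform whether a biomarker sub-aim is feasible in phase 3. Section 7.1 gives every screened person an ID, and section 7.1.2 has exclusion reasons reviewed. No section defines a rate that uses the specimen-visit exclusions.

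**The concern.** A feasibility pilot should tell the phase 3 planner what each requirement costs in recruits. Here the patients most likely to object to specimens can be removed before the blood share is calculated, and both measures in 8.2 are taken after that removal. A good blood share would then describe people who had already agreed to come back for specimens. It would not say how many were lost because specimen visits were required, which is the number needed to decide whether phase 3 should require them.

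The second matter does not depend on criterion 1. A primary outcome with a stated success threshold has two denominators. A patient approached and then excluded under criterion 1 counts in Table 2's denominator but not in that of 8.2. The same recruitment data could therefore meet the 20% threshold on one definition and miss it on the other.

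**Working it through.** **The plan's own figures.** The 50% and 20% values are chosen thresholds without a derivation, so there is nothing to reproduce. With 75 randomised (50 + 25, section 8.7), half is 37.5, so the blood aim needs at least 38. Exactly 20% willingness with 75 randomised implies 75/0.20 = 375 eligible.

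**Assumed inputs.** The documents give no count of specimen-visit exclusions. Let s be the number excluded only for specimen visits, a the share of them who would otherwise accept randomisation, and k = a × s, so k cannot exceed s. I take a = 20%, borrowing the 8.2 threshold, and vary s.

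**Scale of the effect on the blood aim.** Let B be the number of the 75 who agree to give blood. As a worst case only, suppose none of the k would have given blood. The aim then changes from met to missed when B is at least 38 and B/(75 + k) is below 0.5, that is, B is below (75 + k)/2.

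**Two rates that need no assumption about blood.** Specimen-visit acceptance among otherwise eligible patients is 375/(375 + s). Willingness with the s patients added to the denominator only is 75/(375 + s).

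| s | k (a = 20%) | B that would change from met to missed | Specimen-visit acceptance | Willingness, s added to denominator |
|---|---|---|---|---|
| 10 | 2 | 38 (38/77 = 49.4%) | 375/385 = 97.4% | 75/385 = 19.5% |
| 25 | 5 | 38–39 (39/80 = 48.8%) | 375/400 = 93.8% | 75/400 = 18.8% |
| 50 | 10 | 38–42 (42/85 = 49.4%) | 375/425 = 88.2% | 75/425 = 17.6% |
| 100 | 20 | 38–47 (47/95 = 49.5%) | 375/475 = 78.9% | 75/475 = 15.8% |

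For s = 50, the next count up, 43/85 = 50.6%, still meets the aim. If a were 40% with s = 50, k would be 20 and the range would be that of the last row.

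The last column assumes that none of the s patients would have been randomised. If 20% would have been, the rate returns to (75 + 10)/(375 + 50) = 85/425 = 20.0% for s = 50; at 50% it is (75 + 25)/425 = 23.5%. The 20% figure can therefore move either way.

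**Two definitions of willingness.** Take 75 randomised and 375 eligible, so the 8.2 rate is 20.0%. If 450 were approached because some proved ineligible (assumed), Table 2 gives 75/450 = 16.7%. If only 300 were approached because some patients found eligible by record screening were never reached (assumed), it gives 75/300 = 25.0%. The definitions can fall on different sides of the threshold, in either direction.

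**The case against.** The strongest reply is that willingness among randomised patients is a legitimate quantity. A biomarker sub-aim inside phase 3 would draw on randomised participants, Aim 2 is exploratory, and specimen willingness is not an outcome in Table 2. The 50% line is worded as a wish; the success rule is the 20% rate. IDs and exclusion review already exist, and the screening form mentioned in 4.2 is not included in the document and may already split criterion 1. All of this stands, and it keeps the specimen part minor. It does not supply the missing count, because no section commits to separating or reporting it.

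A reader might go further in four ways that the documents do not support:

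- **That criterion 1 guarantees the blood aim.** It does not. The criterion concerns returning for visits; a participant may attend and decline the draw, or agree at entry and refuse later.
- **That the excluded patients should be added to the blood denominator as refusals.** Someone who cannot travel may be quite willing to give blood. B/(75 + k) mixes access with willingness and serves above only as a worst-case scale.
- **That the website and clinic routes code specimen objections differently.** The website is described as "guiding them through simple yes/no eligibility questions to determine if the trial might be right for them", but the documents do not say whether criterion 1 is among those questions, and a clinic objection could equally arise when eligibility is checked. Any difference is conjecture.
- **That the 20% rate is biased in a known direction.** The arithmetic shows it can move either way.

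**Conclusion.** The blood share in 8.2 is conditional on having accepted specimen visits, and the plan neither says so nor isolates the number lost to that requirement. This follows from the text of 4.2, 4.4, 4.5 and 8.2. Its size is unknown. On the stated assumptions (50 specimen-visit-only exclusions, 20% otherwise accepting randomisation, all refusing blood), the reading of the 50% aim changes only for 38 to 42 of 75. Specimen completion will still be informative among those randomised. This part is a minor, cheap improvement.

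The mismatch between Table 2 and 8.2 is a plain inconsistency in a primary outcome that carries a success threshold. It stands whatever is done about criterion 1 and should be corrected.

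**What to change.** Keep criterion 1.

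1. In the existing screening log, record specimen-visit exclusions apart from survey and contact exclusions, with unable and unwilling as separate codes, in the same way on every recruitment route.
2. In 8.2, report that number beside the blood rate among randomised patients and state that the 50% figure is conditional on accepting specimen visits. Add a supplementary specimen-visit acceptance rate: eligible / (eligible + those excluded only for specimen visits). Do not call it a blood-willingness rate.
3. Use one definition of willingness in 8.2 and Table 2 and tie the 20% threshold to it. Randomised over eligible is the natural choice, because the threshold is set there; give enrolled over approached as supplementary. Show a sensitivity rate that adds specimen-visit-only exclusions to the denominator, and note that it assumes none of them would have been randomised.

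The cost is one log field and wording changes in 8.2 and Table 2, with a possibly less favourable feasibility figure. Eligibility, sample size and specimen collection do not change.
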